## 9.4 Analysis of Vital Signs and Weights

Vital sign measurements of pulse rate, sitting systolic blood pressure, and sitting diastolic blood pressure will be summarized.

Each vital sign variable and weight will be summarized for all time points (starting with Baseline) with the number of non-missing observations, mean and standard deviation, median, minimum and maximum. Mean change from baseline to each applicable post-baseline visit will be summarized for each vital sign variable, with the number of observations, baseline mean, and visit mean. The change from baseline mean, standard error, and 95% confidence interval will be presented for the mean change from baseline within each treatment group and difference between elagolix group and placebo.

The number and percentage of subjects who have potentially clinically significant (PCS) vital sign and weight values meeting the following criteria will be summarized by treatment group. All increase/decrease is calculated from Baseline to a post-baseline visit in the Treatment Period.

- Diastolic blood pressure
  - $\circ \leq 50 \text{ mmHg and} \geq 15 \text{ mmHg decrease}$
  - $\circ$  > 90 mmHg and  $\geq$  15 mmHg increase
  - $\circ \geq 100 \text{ mmHg}$
- Systolic blood pressure
  - $\circ \leq 90 \text{ mmHg and} \geq 20 \text{ mmHg decrease}$

- $\circ \geq 140 \text{ mmHg and} \geq 20 \text{ mmHg increase}$
- $\circ \geq 160 \text{ mmHg}$
- Pulse rate
  - $\circ \leq 45$  bpm and  $\geq 15$  bpm decrease
  - $\circ$  > 100 bpm and  $\geq$  15 bpm increase
  - $\circ ~~ \geq 120 ~bpm$
- Weight
  - $\circ \geq 5\%$  decrease
  - $\circ \geq 7\%$  increase.

Listings will be provided to summarize subject-level vital sign and weight data for subjects meeting PCS criteria.

The number and percentage of subjects who had a sustained PCS vital sign and weight values will be summarized by treatment group and a listing of these subjects will be provided. A sustained PCS value is defined as 3 consecutive PCS values.

## 9.5 Other Safety Analyses

## 9.5.1 Columbia Suicide Severity Rating Scale (C-SSRS)

The C-SSRS data will be summarized as observed by treatment group for the Safety Analysis Set.

The C-SSRS – Baseline/Screening measured at Day 1 will be considered as Baseline C-SSRS. Baseline C-SSRS will be summarized. Other analysis of C-SSRS will only include subjects who have at least one post-baseline C-SSRS measurement, regardless of whether they had a baseline C-SSRS measurement. The number of subjects with suicidal ideation, suicidal behavior, and self-injurious behavior without suicidal intent at each scheduled assessment during the appropriate Treatment Period will be summarized. In addition, this table will be repeated for providing a summary of lifetime outcomes and past year outcomes at screening and Day 1. No statistical test will be performed.

The number of subjects with suicide-related treatment-emergent events based on the C-SSRS during the appropriate Treatment Period will be summarized. No statistical tests will be performed.

A listing of subjects with suicidal ideation, suicidal behavior, or self-injurious behavior without suicidal intent based on the C-SSRS during treatment period will be provided.

## 9.5.2 Bone Mineral Density

All analyses and summaries of bone mineral density (BMD) will be performed for each anatomic location, i.e., femoral neck, lumbar spine, and total hip. For subjects who had a right-side scan performed (rare instances), their data for right femoral neck and right femoral total hip will be included in the analysis with the data for the left femoral neck and left total hip, respectively (available for the majority of subjects). If more than one scan is reported for an anatomic location within an analysis window, the worse (the lower value) of the multiple measurements will be used for analysis for each anatomic location. Unless otherwise specified, the analysis of BMD at each post-baseline visit will exclude subjects who switch machine manufacturer type (Lunar or Hologic).

## 9.5.2.1 Bone Mineral Density during the Treatment Period

## BMD

A summary of continuous BMD at each scheduled assessment will be provided during the appropriate Treatment Period. This summary will include the sample size, mean, SD, median, minimum, and maximum. This analysis will be repeated including subjects who switch machine manufacturer type (Lunar or Hologic), for subjects with scans only on Lunar machines, and for subjects with scans only on Hologic machines.

The analysis of percent change in BMD from baseline to each relevant visit during the Treatment Period will be based on an ANCOVA model with treatment as the main effect and baseline value of corresponding parameter as a covariate. Elagolix plus E2/NETA group will be compared to placebo at Months 6 and 12 during the placebo-controlled

Treatment Period. This analysis will be repeated including subjects who switch machine manufacturer type (Lunar or Hologic), for subjects with scans only on Lunar machines, and for subjects with scans only on Hologic machines.

The number and percentage of subjects with percent change from Baseline to each scheduled assessment during the Treatment Period in mutually exclusive categories of BMD decrease:  $\leq 0\%$ ,  $> 0\% - \leq 1.5\%$ ,  $> 1.5\% - \leq 3\%$ ,  $> 3\% - \leq 4\%$ ,  $> 4\% - \leq 5\%$ , > 5% - < 8%, and  $\geq 8\%$  will be summarized by treatment group. Elagolix plus E2/NETA group will be compared to placebo at Months 6 and 12 during the placebo-controlled Treatment Period using a chi-squared test.

Cross-tabulation of the DXA scans performed versus Treatment Period completion will be provided after all subjects complete the Treatment Period or premature discontinue from the Treatment Period.

Listings of subjects meeting the following criteria during the Treatment Period will be provided:

• Listing of subjects with BMD decrease  $\geq 8\%$ 

In addition, the following plot will be provided as needed:

- Percent change from Baseline to each scheduled assessment (Months 6, 12, 18, 24, 30, 36, 42, 48) during the Treatment Period in BMD vs. Baseline BMD values for subjects with greater than 8% BMD decrease at any location during the Treatment Period.
- Cumulative distribution function of percent change from baseline in BMD at each scheduled assessment (Months 6, 12, 18, 24, 30, 36, 42, 48) during the Treatment Period.
- Percent change from Baseline to each scheduled assessment (Months 6, 12, 18, 24, 30, 36, 42, 48) in BMD during the Treatment period.

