### **Bone Mineral Density (DXA Scan)**

DXA scans of the lumber spine, femoral neck and total hip will be performed by qualified technologist/radiologists at the site or affiliated imaging facility utilizing GE Lunar or Hologic equipment and per the acquisition guidelines provided by the Central Imaging Core Lab (central reader). The DXA technologist/radiologist or designee for each investigative site should electronically submit the subject's DXA images to the central reader for review and analysis following acquisition. Subject eligibility and treatment management will be made based on the central reader review. Sites will receive reports from the central reader detailing the results (including T-scores and BMD % change from baseline, as applicable) of the DXA scans performed. Site training and qualifications, including assessment of instruments, will be evaluated/approved by the central reader prior to screening the first subject. Instructions on calibration and standardization of instruments and any additional required information will be specified in a manual from the central reader that will be provided to all study sites. Sites will need to obtain approval from the central reader prior to initiating study scans.

A DXA scan will be performed during Screening Period and sent to the central reader to determine eligibility and serve as the baseline scan for subject management. Subjects with a T-score of < -2.0 at the lumber spine, total hip **or** femoral neck on the screening DXA scan will not be eligible to enter the study.

During the Treatment Period, DXA scans will be performed for all subjects at Months 6, 12, 18, 24, 30, 36, 42 and 48 and will be submitted to the central reader for review and analysis. The central reader will be blinded to the subject's treatment assignment (in the 12-month Treatment Period), but not to the corresponding time point.

[figure not shown]
If the results of any post-baseline DXA prior to and including Month 48, as read by the central reader selected for the study, document a T-score of < -2.5 in the lumbar spine, total hip **or** femoral neck, the subject must be discontinued from study drug dosing and will enter the Follow-Up Period.

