Subjects with a BMD decrease of > 8% in the lumbar spine, total hip, or femoral neck (any of the three regions) on any DXA scan performed during the Treatment Period (i.e., Months 6, 12, 18, 24, 30, 36, and 42) must be discontinued from study drug dosing and will enter the Post-Treatment Follow-Up Period.

DXA scans are also required if a subject premature discontinues for the following reasons:

- Subjects who discontinue prior to the Treatment Month 6 visit only if the reason for premature discontinuation is due to the occurrence of a fracture or any newly diagnosed bone condition
- Subjects who discontinue any time at the time of or after the Treatment Month 6 visit unless a DXA scan has been performed within 3 months of Premature Discontinuation.

However, if a subject is being discontinued from the study due to a T-score of < -2.5 in any region (the lumber spine, total hip or femoral neck), BMD decrease from baseline of > 8% in any region, or TA MD assessment, additional DXA scans do not need to be performed as a part of the Premature Discontinuation visit procedures. In these circumstances, the subject would enter into the Post-Treatment Follow-Up Period and continue with required BMD evaluations.

DXA scans of the lumbar spine, total hip, and femoral neck will be obtained at Post-Treatment Follow-Up Period at Months 6 and/or 12, except for subjects who prematurely discontinued less than 3 months during the Treatment Period.

If the BMD percent change from baseline of any post-baseline DXA cannot be provided by the central reader (i.e., due to scanner changes), then the TA MD must be consulted to confirm if the subject can continue study drug dosing. A BMD decrease at any anatomic location (lumber spine, total hip **or** femoral neck) that results in discontinuation from the study should be reported as an adverse event (Section 6.1.1).

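### The pooled Month 6 and Month 12 BMD model has no scanner-manufacturer term, which may cost a little precision

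*SAP*

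**What the plan says.** Protocol 5.3.1.1 (Bone Mineral Density) has sites scan "utilizing GE Lunar or Hologic equipment". It leaves calibration and standardisation of instruments to a central-reader manual that is not among the documents. Protocol 8.1.7.4 leaves the form of the BMD model to the SAP.

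In SAP 9.5.2.1, "The analysis of percent change in BMD from baseline to each relevant visit during the Treatment Period" rests on an "ANCOVA model with treatment as the main effect and baseline value of corresponding parameter as a covariate". The between-arm comparison is at Months 6 and 12. Manufacturer does not appear in the model.

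Three other provisions bear on the point:

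- SAP 9.5.2 says that, unless otherwise specified, the BMD analysis at each post-baseline visit "will exclude subjects who switch machine manufacturer type (Lunar or Hologic").
- SAP 9.5.2.1 repeats the same ANCOVA with the switchers included, and then "for subjects with scans only on Lunar machines, and for subjects with scans only on Hologic machines".
- Protocol 5.5.3 describes central randomisation and names no stratification factor, so nothing described balances scanner type between arms.

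SAP 9.5.2.2 uses the same model in follow-up but makes no comparison between groups there.

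**The concern.** The outcome is each woman's percent change from her own baseline, so a proportional difference between the two scales largely cancels from it. It does not cancel from the covariate, which is the baseline BMD value itself. If one manufacturer reads systematically higher, the pooled covariate is a mixture of true bone density and machine type. One slope fitted to that mixture is flatter than the slope within either manufacturer. Two things follow:

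- Less of the outcome variance that baseline could explain is removed.
- A chance difference between arms in scanner mix is adjusted as if it were a difference in bone density.

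Months 6 and 12 are the only randomised, tested BMD comparisons in the study, and bone is central to its objectives. What is at stake is a small amount of precision in those two comparisons.

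**Working it through.** **Plan's own figure.** There is none to reproduce for BMD. The sample size of 500 was set by clinical review (Protocol 8.2, SAP 2.4), with no BMD effect, SD or power. A 2:1 split of 500 is 333.3 to 166.7. The protocol has 335/165 and the SAP 333/167. The protocol's split is used below.

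**Inputs that are not in the documents (assumed).** Half the women on each manufacturer; Lunar mean 1.10 g/cm2; within-manufacturer baseline SD 0.12 g/cm2; SD of percent change 3 points; baseline slope 0.3 to 1.0 points per SD; a Lunar-Hologic shift of 0 to 20%.

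**Step 1: how far the covariate is diluted.** Let v be the within-manufacturer variance, 0.12² = 0.0144, and d the offset between scales. With a 50:50 mix, the share of covariate variance that is within manufacturer is λ = v / (v + 0.25d²).

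- 5% shift: d = 0.055, λ = 0.0144/0.01516 = 0.95
- 12% shift: d = 0.132, λ = 0.0144/0.01876 = 0.77
- 20% shift: d = 0.220, λ = 0.0144/0.02650 = 0.54

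**Step 2: effect on the standard error.** Let σ² be the residual variance of the model with a manufacturer term and β the slope per g/cm2. Without the term the residual variance is σ² + β²v(1 − λ), so

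SE ratio = √[1 + β²v(1 − λ)/σ²].

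For a slope of 1.0 point per SD, β²v = 1 and σ² = 9 − 1 = 8. A 12% shift gives √(8.232/8) = 1.014, and a 20% shift gives √(8.457/8) = 1.028. Simulation of both models (335 v 165, 3,000 trials per setting) agrees:

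| Shift | Slope per SD | SE without term | SE with term | Change |
|---|---|---|---|---|
| 0% | 0.3 | 0.2838 | 0.2841 | +0.1% |
| 5% | 1.0 | 0.2698 | 0.2692 | −0.2% |
| 12% | 0.3 | 0.2842 | 0.2841 | 0.0% |
| 12% | 1.0 | 0.2736 | 0.2697 | −1.4% |
| 20% | 1.0 | 0.2777 | 0.2697 | −2.9% |
| 12%, plus a 1-point direct machine effect on percent change | 0.6 | 0.2887 | 0.2803 | −2.9% |

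The first row shows the price of the term when it is not needed.

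**Step 3: an extreme case.** Take 210 v 105 evaluable women, residual SD 2.5, offset 0.20 g/cm2 and slope −12 points per g/cm2 (all assumed). Then λ = 0.0144/0.0244 = 0.590, β²v = 144 × 0.0144 = 2.07, and the ratio is √(7.10/6.25) = 1.066, a reduction of 1 − 1/1.066 = 6.2%. Simulation gave 0.319 without the term and 0.300 with it, a reduction of 6.0%. This case needs baseline BMD to explain 2.07/(2.07 + 6.25) = 25% of the within-arm variance in percent change.

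**Step 4: bias and coverage.** In the 335/165 simulations without imposed imbalance, the mean error of the treatment estimate was below 0.007 points with or without the term. That is about the simulation error, 0.28/√3000 = 0.005. Coverage of the 95% interval without the term was 94.3 to 95.7%.

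**Step 5: chance imbalance in scanner mix.** A 10-point difference between arms in the share on one manufacturer was imposed, with a 12% shift. The estimate without the term moved by about 0.03 to 0.09 points against a standard error of about 0.28, and coverage was 93.6 to 95.1%. Under a 50:50 mix the SD of a chance difference in share is √[0.25(1/335 + 1/165)] = 4.8 points, so 10 points is about two SDs.

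**The case against.** The strongest reply is that the model is valid as it stands and that the plan already looks at manufacturer. Most of this is right.

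- **Consistency.** A reader might infer that the SAP contradicts itself by excluding switchers as not comparable and then pooling both machines. The documents do not support that. A switcher's percent change would mix two machines, and Protocol 5.3.1.1 has the same worry when it says "If the BMD percent change from baseline of any post-baseline DXA cannot be provided by the central reader (i.e., due to scanner changes"). A woman who stays on one manufacturer has no such problem, so the two rules fit together.
- **Bias.** A reader might also infer a biased comparison or an inflated error rate. Randomisation prevents the first, and the coverage in Step 4 shows no sign of the second.
- **Two harms or one.** The movement of a single trial's estimate and the loss of precision are largely the same quantity. In the extreme case √(0.319² − 0.300²) = 0.108 points, which is the typical movement. The reported interval already carries it.
- **Unconverted readings.** The SAP says only that the baseline value is used. A conversion in the central reader's manual cannot be ruled out, though none is described.
- **The planned repeats.** The Lunar-only and Hologic-only analyses put the covariate on one scale and will show whether manufacturer matters. They give two smaller estimates with no planned combination, so they do not sharpen the pooled comparison.

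What survives is the small loss of precision in the pooled model.

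**Conclusion.** The point holds as a minor refinement. The pooled Month 6 and Month 12 ANCOVA leaves out a factor that could improve the baseline adjustment, and the planned single-manufacturer repeats do not recover that precision in the pooled estimate. The expected gain is a standard error lower by about 0 to 3%, and by about 6% only where a large offset and a steep baseline slope coincide. Every figure depends on an assumed scale difference, machine mix, slope and SD. If the scales barely differ or baseline hardly predicts change, the gain is nil. The study has no BMD power target or margin that a change of this size would affect. The point does not extend to SAP 9.5.2.2, where there is no between-group estimate to sharpen.

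**What to change.** In SAP 9.5.2.1, add baseline scanner manufacturer as a factor in the pooled ANCOVA at Months 6 and 12, or centre baseline BMD within manufacturer. Keep the planned Lunar-only and Hologic-only repeats as sensitivity analyses. Leave 9.5.2.2 unchanged. If the central reader's manual already converts between manufacturers, one sentence in the SAP saying so would settle the point.

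The cost is negligible: one degree of freedom for the factor, two if each manufacturer also gets its own slope. No new data are needed, because manufacturer must already be known to apply the switcher rule and run the repeats. Timing matters: SAP 2.5 makes the end-of-12-month analysis the only and final comparison with placebo, and the SAP is dated January 2021. If that analysis has been run, keep its result and report the adjusted model as a labelled sensitivity analysis.

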#### Z-Score and T-Score

A continuous summary of the Z-score and T-score at each scheduled assessment will be provided by treatment group during the Treatment Period. This summary will include the sample size, mean, SD, median, minimum, and maximum.

A categorical summary of Z-score will be provided at each scheduled assessment during the Treatment Period for the following categories:  $\leq -2.0$ ,  $\geq -2.0$  to  $\leq -1.5$ ,  $\geq -1.5$  to  $\leq -1.0$ , and  $\geq -1.0$ . A categorical summary of T-score will be provided at each scheduled assessment during the Treatment Period for the following categories:  $\leq -2.5$ ,  $\geq -2.5$  to < -1.0, and  $\geq -1.0$ . In addition, a categorical summary of the worst Z-score and T-score during the Treatment Period for the above categories will be provided.

## 9.5.2.2 Bone Mineral Density during the Follow-up Period

#### **BMD**

A summary of continuous BMD at each scheduled assessment will be provided by treatment group during the Follow-up Period. This summary will include the sample size, mean, SD, median, minimum, and maximum. This analysis will be repeated including subjects who switch machine manufacturer type (Lunar or Hologic), for subjects with scans only on Lunar machines, and for subjects with scans only on Hologic machines.

The analysis of percent change in BMD from baseline to each relevant visit during the Follow-up Period will be based on an ANCOVA model with treatment as the main effect and baseline value of corresponding parameter as a covariate. No comparison will be performed during the Follow-up Period. This analysis will be repeated including subjects who switch machine manufacturer type (Lunar or Hologic), for subjects with scans only on Lunar machines, and for subjects with scans only on Hologic machines.

The analysis of percent change in BMD from baseline will be repeated for the following subset of subjects:

• subjects who have a Treatment Month X (e.g., Month 12) scan and a Follow-up Month Y (e.g., Follow-up Month 6) scan and premature discontinue prior to next scheduled assessments.

The number and percentage of subjects with percent change from Baseline to each scheduled assessment during the Follow-up Period in mutually exclusive categories of BMD decrease:  $\leq 0\%$ ,  $> 0\% - \leq 1.5\%$ ,  $> 1.5\% - \leq 3\%$ ,  $> 3\% - \leq 4\%$ ,  $> 4\% - \leq 5\%$ , > 5% - < 8%, and  $\geq 8\%$  will be summarized by treatment group.

In addition, the number and percentage of subjects with percent change from final ontreatment to each scheduled assessment during the Follow-up Period in mutually exclusive categories of BMD decrease:  $\leq 0\%$ ,  $> 0\% - \leq 1.5\%$ ,  $> 1.5\% - \leq 3\%$ ,  $> 3\% - \leq 4\%$ ,  $> 4\% - \leq 5\%$ , > 5% - < 8%, and  $\geq 8\%$  will be summarized by treatment group.

For the purpose of assessing post-treatment BMD recovery, the following summaries will be provided. The "recovery" statistic was defined as:

Recovery at Follow-up Month  $X = 100 \times ((\% \text{ change from baseline to final}) - (\% \text{ change from baseline to Follow-up Month X}))/(\% \text{ change from baseline to final})$ 

The "recovery" statistic is the proportion of BMD decrease at the final treatment scan recovered at Follow-up Month X. For example, a subject who has a change of -2% at the end of treatment and has a change of -1% at Follow-up Month 6 has a recovery value of 50% at Follow-up Month 6. This statistic will only be defined for subjects who experienced a decrease from baseline at final treatment.

A continuous summary of recovery at each relevant visit during the Follow-up Period will be provided including mean, standard deviation, median, and a within-group 95% confidence interval for the following subset of subjects:

- All subjects who experienced a decrease from baseline at final treatment;
- Subjects who premature discontinue after Month 6 and on or prior to Month 12;

- Subjects who premature discontinue after Month 12 and on or prior to Month 18;
- Subjects who premature discontinue after Month 18 and on or prior to Month 24;
- Subjects who premature discontinue after Month 24 and on or prior to Month 30;
- Subjects who premature discontinue after Month 30 and on or prior to Month 36;
- Subjects who premature discontinue after Month 36 and on or prior to Month 42;
- Subjects who premature discontinue after Month 42 or completed the Treatment Period.

Additionally, the number and percentage of subjects in each of the following categories will be provided for the subset of subjects listed above: < 0%, 0 - 25%, > 25 - 50%, > 50 - 75%, > 75 - 100%, > 100%.

Bone loss will be defined as > 3% at the spine, > 4% at the total hip, or > 5% at the femoral neck. The following listings will be provided:

• Listing of subjects with bone loss from baseline to final on-treatment visit and continued bone loss from final on-treatment to Follow-up visits will be provided. Subjects subsequently with an increase from Follow-up Month 6 to a subsequent Follow-up assessment will be excluded from this listing.

In addition, the following plots will be provided:

- Cumulative distribution function of recovery at Follow-up Month 6 and Follow-up Month 12.
- Percent change from baseline to treatment and follow-up months of interest.

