#### Methodology:

This Phase 3b, sequential, randomized, 12-month double-blind placebo-controlled, 36-month open-label, multi-center study is designed to evaluate the long term safety of elagolix with add back therapy in women with HMB associated with uterine fibroids. Approximately 500 subjects will be randomized in a 2:1 ratio to one of the following two treatment groups:

- 1. Elagolix 300 mg BID plus E2/NETA (estradiol 1.0 mg/norethindrone acetate 0.5 mg QD) (n = 335) for 48-months
- 2. Placebo (n = 165) for 12-months, followed by elagolix 300 mg BID plus E2/NETA (estradiol 1.0 mg/norethindrone acetate 0.5 mg QD) for 36-months

[figure not shown]
Subjects randomized to elagolix 300 mg BID plus E2/NETA in the 12-month Treatment Period will receive the same treatment during the open label Treatment Period. Subject randomized to placebo in the 12-month Treatment Period will switch to elagolix 300 mg BID plus E2/NETA during the open label Treatment Period after completing the 12-month Treatment Period.

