#### Post-Treatment Follow-Up Period:

Subjects will enter the Post-Treatment Follow-Up Period for up to 12 months to assess bone recovery after up to 48 months of treatment. Subjects who prematurely discontinue from the study at any time during the Treatment Period will enter the Post-Treatment Follow-Up Period. DXA scans of the lumbar spine, total hip, and femoral neck will be obtained at Post-Treatment Follow-Up Months 6 and/or 12.

Pregnancy testing, samples for FSH and E2, Return to Menses questionnaire completion will be performed at designated study visits. Adverse events and concomitant medication use will also be reviewed. Subjects may begin taking hormonal contraceptive preparations only after completing the open-label Treatment Period, being off study drug for 30 days, having a negative urine pregnancy test and returning to menses.

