#### Post-Treatment Follow-Up Period

Subjects will enter the Post-Treatment Follow-Up Period for up to 12 months to assess bone recovery after up to 48 months of treatment. Subjects who prematurely discontinue

from the study at any time during the Treatment Period will enter the Post-Treatment Follow-Up Period.

Adverse event collection and concomitant medication review is detailed in Section 6.1.4 and Appendix C.

[figure not shown]
DXA scans and additional detail regarding study procedures during the Post-Treatment Follow-Up Period is provided in Section 5.3.1.1 and Study Activities, Appendix C.

Study visits may be impacted due to the COVID-19 pandemic. This may include changes such as phone or virtual visits, visits at alternative locations, or changes in the visit frequency and timing of study procedures, among others. Additional details are provided for certain procedures. Every effort should be made to ensure the safety of subjects and site staff, while maintaining the integrity of the study. If visits cannot be conducted onsite due to travel restrictions or other pandemic-related reasons, study visits may be conducted over the phone where feasible and AbbVie should be notified.

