#### Figure 1.Study Schematic (Continued)

#### TREATMENT AND POST-TREATMENT FOLLOW-UP PERIOD

## 2.3 Treatment Assignment and Blinding

Approximately 500 subjects will be randomily assigned in a 2:1 ratio to one of the following 2 treatment groups:

- Elagolix 300 mg BID plus E2/NETA (estradiol 1.0 mg/norethindrone acetate 0.5 mg QD) (n = 333)
- 2. Placebo (n = 167)

Unless otherwise specified, data will be summarized by group as listed above.

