# 4.0 Analysis Populations

The Full Analysis Set (FAS) is composed of all randomized subjects who have received at least 1 dose of study drug in this study. The data from the FAS will be presented by the treatment group assigned at the time of randomization, even if a subject does not receive the correct treatment or does not follow the protocol until completion. The FAS will be used for all efficacy and baseline analyses unless otherwise specified in the SAP. Subjects who do not continue into the open-label Treatment Period will be excluded from the analyses in the open-label Treatment Period.

The following populations will be used for safety analyses:

- The Safety Analysis Set includes all randomized subjects who received at least 1 dose of study drug. Subjects will be analyzed according to the treatment they actually receive, defined as the randomized treatment if the patient took at least one dose of that randomized treatment during the 12-month placebo-controlled double-blind Treatment Period, or the first treatment received if the randomized treatment was never received during the 12-month placebo-controlled doubleblind Treatment Period. Subjects who do not continue into the open-label Treatment Period will be excluded from the analyses in the open-label Treatment Period.
- The All Elagolix plus E2/NETA Analysis Set is defined as subjects who received at least 1 dose of elagolix plus E2/NETA in the study (either in the placebo-controlled or open-label Treatment Periods). Subjects will be summarized based on the actual treatment received at the time of randomization (elagolix plus E2/NETA or placebo).

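### Unstratified follow-up BMD tables and the overall recovery row pool placebo-randomised women never given elagolix with switchers who took it for up to 36 months

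*SAP*

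**What the plan says.** The protocol (5.1, Post-Treatment Follow-Up Period) gives the purpose of follow-up as "to assess bone recovery after up to 48 months of treatment". SAP 9.5.2.2 sets the grouping: "A summary of continuous BMD at each scheduled assessment will be provided by treatment group during the Follow-up Period". The same section fits percent change from baseline by ANCOVA with treatment as the main effect. It also tabulates BMD-decrease categories by treatment group, once from baseline and once from the final on-treatment scan.

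Three rules determine who is in each group:

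- SAP 2.3 lists the two randomised arms and adds: "Unless otherwise specified, data will be summarized by group as listed above".
- SAP 4.0 analyses the Safety Analysis Set by treatment actually received, but this is "defined as the randomized treatment if the patient took at least one dose of that randomized treatment". After one correct dose it is the randomised arm.
- The protocol synopsis (Methodology) describes the second arm as "Placebo (n = 165) for 12-months, followed by elagolix 300 mg BID plus E2/NETA", the active part lasting 36 months.

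On entry to follow-up, the synopsis says: "Subjects who prematurely discontinue from the study at any time during the Treatment Period will enter the Post-Treatment Follow-Up Period". Protocol 5.3.1.1 (DXA) requires follow-up scans "except for subjects who prematurely discontinued less than 3 months during the Treatment Period".

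Recovery is summarised for one overall subset ("All subjects who experienced a decrease from baseline at final treatment") and for seven bands of stopping time, from after Month 6 up to Month 12 through to after Month 42 or completion.

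**The concern.** Together these rules give a placebo column in which elagolix exposure at the start of follow-up runs from 0 to 36 months. Its mean shows neither recovery after elagolix nor the course in an untreated group. If unexposed women lose less bone, pooling makes the loss in switchers look smaller. BMD over up to 48 months is one of the study's two objectives, and follow-up is where recovery is read.

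The reference point is also open. SAP 9.1 gives a baseline for the placebo-controlled period, for the open-label period and for the All Elagolix plus E2/NETA Analysis Set, but none for follow-up. For a switcher the candidates are about 12 study months apart.

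**Working it through.** **Nothing in the plan to reproduce.** The plan gives no figure for the make-up of the follow-up groups and no dropout rate. Its only related figures are the 2:1 split (500 x 2/3 = 333.3, so 333/167 in the SAP; the protocol has 335/165) and about 50 completers at 48 months, chosen on clinical review. The size below is therefore an illustration.

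**Who is mixed, output by output (SAP 9.5.2.2, placebo-randomised women)**

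- BMD, percent-change and category tables: all women with a follow-up scan, 0 to 36 months of elagolix. Mixed.
- Percent change repeated by last treatment scan: the Month 6 subset is never exposed, and subsets from Month 18 on are switchers. The Month 12 subset can hold both women who did not enter open label and women who stopped early in it.
- Recovery, overall row: mixed. The recovery distribution plot is mixed too unless it is stratified, which the SAP does not say.
- Recovery, seven bands: the first is never exposed, apart from boundary cases at Month 12; the other six are switchers. The bands count study months. After Month 12 up to Month 18 means 12 to 18 months of elagolix in one arm and 0 to 6 in the other.

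**Size of the mixing.** Inputs: N = 165 placebo women (protocol); Year 1 dropout d, assumed 15% to 45%; constant attrition within the year, assumed; no follow-up DXA for women treated under 3 months (Protocol 5.3.1.1); everyone due a scan has it, assumed.

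- Women due a follow-up DXA: N x (1-d)^(1/4)
- Of these, never exposed: N x [(1-d)^(1/4) - (1-d)]
- Never-exposed share: f = 1 - (1-d)^(3/4)
- Pooled mean if switchers average -2% and unexposed women 0% (assumed): -2% x (1-f)

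| d | never exposed, due DXA | share f | pooled mean |
|---|---|---|---|
| 15% | 18 | 11.5% | -1.77% |
| 25% | 30 | 19.4% | -1.61% |
| 35% | 41 | 27.6% | -1.45% |
| 45% | 51 | 36.1% | -1.28% |

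As a cross-check, constant attrition to the planned completers (50/500 = 10% overall, or about 20/165 = 12% in the placebo arm) gives Month 12 retention of 0.10^(1/4) = 56% to 0.12^(1/4) = 59%. The share is then 33% to 35%, inside the range.

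**Recovery.** Women who stop before Month 6 have a discontinuation DXA only for a fracture or new bone condition, so they generally have no on-treatment scan. The share becomes 1 - (1-d)^(1/2), or 8% to 26%, before the further restriction to women with a decrease.

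**Baseline (invented values).** Take a switcher with BMD 1.000 at Day 1, 0.990 at Month 12, 0.970 at the final treatment scan and 0.980 at follow-up.

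- From Day 1: changes of -3.0% and -2.0%; recovery 100 x (3.0 - 2.0)/3.0 = 33%.
- From Month 12: changes of -2.02% and -1.01%; recovery 50%.

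If Month 12 were 1.010 and the final scan 1.000, she shows no decrease from Day 1, so recovery is undefined. From Month 12 she shows -0.99% and is counted. The baseline changes both the value and who contributes.

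**The case against.** The strongest reply is that the SAP already contains most of the remedy. SAP 9.1 plans safety summaries on the All Elagolix plus E2/NETA Analysis Set, which excludes never-exposed women and takes baseline at the start of elagolix. Protocol 8.1.5 gives a default baseline before study drug. The stopping-time bands and the repeat by last treatment scan do much of the separating. A reader who knows the design can subtract 12 months in the placebo column. Follow-up is descriptive, with no comparison planned.

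Much of this stands. A reader might infer that recovery is pooled throughout; seven of the eight recovery subsets show otherwise. A reader might also take the never-exposed share as all Year 1 placebo dropouts, 15% to 45% of the arm on the same assumption. That ignores the exemption for women treated under 3 months and overstates the share. Nor do the documents support any effect on a test.

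What does not stand is that the existing text settles the matter. SAP 9.5.2.2 names no analysis set, and SAP 9.1 does not link the All Elagolix set to follow-up. SAP 4.0 removes non-continuers from open-label analyses only, and Protocol 8.1.1 defines continued and switched groups only for that period. The two default baselines conflict for a switcher: the protocol's is before Day 1, the All Elagolix set's is at the start of elagolix.

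**Conclusion.** The point holds for the unstratified follow-up BMD, percent-change and category tables, the overall recovery row, and the recovery distribution plot if unstratified. On the default grouping, each pools placebo-randomised women with 0 to 36 months of elagolix. The missing follow-up analysis set and baseline are a further gap. The baseline gap does not touch the category table measured from the final on-treatment scan, though that table is still mixed.

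As a guide to size, about 11.5% to 36% of placebo-arm women due a follow-up DXA would be never exposed, and an assumed -2% in switchers would read about -1.8% to -1.3%. These figures rest on assumed dropout of 15% to 45%, constant attrition, full scan attendance and no change in unexposed women; none comes from the documents. The share is smaller for recovery. The consequence is limited to how descriptive safety results are read.

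**What to change.** In SAP 9.5.2.2:

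1. Name the All Elagolix plus E2/NETA Analysis Set for the follow-up BMD and recovery summaries, with the baseline SAP 9.1 already gives it (last value on or before the day elagolix starts). That set's split by treatment at randomisation then gives a continued column and a switched column.
2. Show placebo-randomised women who never took elagolix in a separate column, from the Safety Analysis Set with the Day 1 baseline.
3. Label or band the recovery subsets by months on elagolix at stopping. Apply the same split to the Month 12 scan subset and the recovery distribution plot.

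The cost is SAP wording, a few more tables and somewhat smaller subgroups. No new data are needed.
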